Source: AT Ayance, HS Ramírez, JMR Pérez and CGT Palacios, "Low-cost microcontrolled based wireless heart rate and oxygen saturation monitor," 2018 International Conference on Electronics, Communications and Computers (CONIELECOMP), 2018, pp. 176-180, doi: 10.1109/CONIELECOMP.2018.8327195.

The rPPG on the other hand works on the same basic principle as the PPG in reflection except that the ambient light plays the role of the LED and the camera the role of the photodetector (see figure 2).

[figure not shown]

Figure 2. Light path in skin for a) contact PPG b) remote PPG

Source: Verkruyse, Wim PhD*; Bartula, Marek MSc†; Bresch, Erik PhD‡; Rocque, Mukul MSc†; Mestah, Mohammed BSc†; Kirenko, Ihor PhD† Calibration of Contactless Pulse Oximetry, Anesthesia & Analgesia: January 2017 - Volume 124 - Issue 1 - p 136-145 doi: 10.1213/ANE.0000000000001381

In its current version, the technologies embedded in this SaaS platform (COBOX) allow remote tracking, calculation and processing of several biological markers (cardio-respiratory rate). The idea is therefore to transform any camera into a medical device. From this camera. It is a SaaS platform type product that can be integrated and integrated into any other existing or future device. The data can be sent to the patient and the practitioner or managed in real time by trained and qualified nursing staff.

Finally, for its operation, the SaaS API requires a high-speed internet connection and an image capture device by optical camera.

The objectives of this solution are multiple:

- Standardization & reproducibility of the measurement :

Taking the constant "manually" by observation is today the reference method for measuring the respiratory rate. According to good training practices for medical or paramedical nursing staff, this method consists of counting the respiratory movements (inspiration and expiration) of the rib cage for 30 seconds extrapolated to 1 minute (by multiplying the value by two). This technology makes it possible to standardize the measurement of the respiratory rate by a reproducible and repeatable method with considerably reduced operator bias.

- Save time by automating vital signs measurements

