In current practice, measurements of respiratory rhythms and frequencies are taken visually by identifying the movements of the rib cage: The operator (nursing staff or arc or medical or paramedical tec) in current practice counts the complete respiratory movements (inspiration + exhale) for 30 seconds and multiply by 2 to extrapolate the result to 1 minute (Cycles per minute).

This medical decision-making can therefore vary according to these results, 2 to 3 cycles per minute varying around a "risk zone" (Above 20 cycles/minute or below 12/minute) can decide to whether or not to put on oxygen (these results are always interpreted with the oxygen saturation). Beyond the lack of robustness and reproducibility of this measurement in routine care, the purely human intervention makes its regular or continuous monitoring complex and time-consuming.

Finally, this data without a real monitoring standard is data that is almost unusable in epidemiological and/or clinical research.

Potential side effects

There are no direct or indirect adverse effects for the patient identified to date.

Residual risks associated with the experimental device, as identified in the risk analysis report

After implementation of risk reduction actions (in accordance with document REC-M2-016 Product risk analysis of the Technical File), all the residual risks assessed are deemed acceptable.

Risks associated with participating in the clinical investigation

No associated risk has been identified, the non-inclusion measures having been identified in this regard. The data collected for the evaluation will be observational and the information provided by COBOX will not be used in clinical decision-making.

Possible interactions with concomitant medical treatments

No interactions have been identified.

Measures that will be taken to control or mitigate the risks

The COBOX application poses no risk to the patient.

Justification of the risk/benefit ratio

As stated previously, the implementation of the risk management process led to the absence of unacceptable residual risks for the conduct of this study. Furthermore, the assessment of the benefit/risk is the subject of provisions documented within the PRO-M2-004 Risk Management procedure.

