- Patient having constant FC and FR taken by the nursing staff (or arc or tec) of emergency reception
AND
- Patient who did not express his opposition to participate in the study
AND

- Patient affiliated to a social security scheme

Non-inclusion criteria

- Patient in a state of vital emergency with direct entry into SAUV or intensive care.
- Patient unable to express consent.
- Patient unable, for health reasons, to face the COBOX tool.
- Patient unable to stand for 30 seconds facing the COBOX solution.
- Patient with skin stigma over more than 50% of the face (burn, graft)
- Patient with the face covered or not allowing access to the entire face (clothing)

Recruitment methods

In order not to delay the care of patients in the emergency room, recruitment is carried out by the IOA (or arc or tec) at the time of their usual care. She communicates oral information to the patient on the use of the tool during the measurements and presents the consent letter in electronic format in the tablet. If the patient gives consent, the test is performed. In case of opposition, the COBOX device will not be used.

It is therefore a serial recruitment, without selection of the participants.

7. Experimental device(s) and comparator(s)

Description of exposure to comparators

In order to standardize the measurements of the four hospital centers, QUANTIQ will provide each center with a CMS60D digital pulse oximeter from the Contec brand. This device is CE marked and commonly used in hospitals. This device will be used at the same time as the CE marked device used during the reference technical process of the hospital center, without modifying the practices of each center. The comparison of results will be between the Contec CMS60D and the COBOX tool.

Device	Acquisition cost	Trolley (300 to 700 Euros)	Whip Set and Monobase Cables	Lifespan (Year)	Annual Maintenance Cost	Annual cost for 1 technical platform
Contec CMS60D Digital Pulse Oximeter (SpO2 - Heart Rate)	242.50 €	N / A	N / A	2 YEARS (AVERAGE)	Replaced/No Maintenance - PURCHASE Management (12.1 €)	133.4 €

List of any other medical device or drug that will be used during the clinical investigation.

The Contec CMS60D reference DM will be provided by Quantiq while COBOX will be installed on a Samsung S6 tablet also provided by Quantiq.

Number of experimental devices to be used, along with a rationale

3 reference Contec CMS60D oximeters will be provided per center.

Treatment(s)/ management of experimental devices

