
QUANTIQ provides users with one tablet per site per physician. Delivery of a functional tablet in the event of a malfunction within 5 working days. Bug fix within 3 days in case of software malfunction with continuous information for professionals.

8. Research process

Research timeline

- Start of inclusions: Mid-July 2022
- Duration of the inclusion period: 2 months
- Duration of participation of each patient: The time of their passage in the IOA box (less than 30 minutes)
- Total research duration: 3 months

Summary of patient follow-up

- Oral information by the IOA. If necessary, an investigating physician can complete the information at the patient's request.
- Informed consent with electronic signature.
- Collection of the patient's age, gender and Fitzpatrick phototype.
- Collection of patient identification number.
- The nursing staff (or arc or tec) installs the oximeter on the patient's finger.
- The nursing staff (or arc or tec) starts COBOX and begins to count the breaths in parallel.
- After 15s, a first measurement is made by COBOX. The pulse oximeter reference result is acquired in parallel, associated with the patient ID number and stored with the COBOX result at the same time on an electronic database.
- After 20s (5s after the previous measurement), a second measurement is made by COBOX. The pulse oximeter reference result is acquired in parallel, associated with the patient ID number and stored with the COBOX result at the same time on an electronic database.
- After 25s (5s after the previous measurement), a third measurement is made by COBOX. The pulse oximeter reference result is acquired in parallel, associated with the patient ID number and stored with the COBOX result at the same time on an electronic database.
- After 30s, the nursing staff (or arc or tec) enters the number of breaths counted since the start. This result is converted into a respiratory rate (RR) then associated with the patient number and stored in the database.

The data is blocked on the database until the end of the study. At the end of the study, they will be sent to the coordinating centre.

In order not to disrupt the general operation of the emergency department and patient care, the usual patient circuit is not modified. The COBOX tool is used by the reception staff in a contemporary way to their usual collection of input parameters.

Collection of consent

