The information is compiled by the IOA and if necessary completed by a doctor. This information must make it possible to answer all the patient's questions concerning the objective, the nature of the constraints, the foreseeable risks and the expected benefits of the research. It also specifies the patient's rights in the context of a clinical investigation and verifies the eligibility criteria. A copy of the information note and the electronic consent form are then given to the patient by the investigating physician.

The consent form is electronic and must be signed before data can be collected for research. After electronic acceptance of the consent, a copy of the consent form is sent to the patient with his identification number allowing him at any time to ask the Sponsor to delete his data. For his part, the Sponsor only has access to the patient's identification number but his email address is not stored.

The data will include:

- Taking FC and FR by the reference method
- HR and FR taken by the COBOX tool at the same time as those of the reference tool.
- The patient's age, sex and Fitzpatrick phototype.

The different copies of the information notice and the consent form are then distributed as follows:

- A copy of the information note and the signed consent is given/sent by email to the patient.
- The original copy is kept by the investigating physician (even if the patient moves during the duration of the research) in a safe place inaccessible to third parties.
- When accepting the patient's participation on the electronic form. This is automatically sent to the Sponsor.

Search stopping rules

The temporary stoppage of the research can be pronounced by technical problems concerning the evaluated tool. The research stops definitively when the necessary number of subjects is reached and all the data allow the analysis.

Constraints related to research and possible compensation of subjects/patients

Patients can simultaneously participate in another research. No compensation is provided for in this study. The patient will not be registered in the national file of people who lend themselves to biomedical research.

9. Management of adverse events and new facts

In accordance with article 2 of regulation 745/2017, the following terms mean:

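### No listed COBOX reading spans the 30 s breath count, and the COBOX respiratory-rate value to compare with it is not named; a value covering 0–30 s should be recorded and pre-specified

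*Combined protocol and SAP*

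**What the plan says.** The sequence is in section 8, Summary of patient follow-up. COBOX and the count begin together: "The nursing staff (or arc or tec) starts COBOX and begins to count the breaths in parallel". COBOX readings follow at 15 s, 20 s and 25 s, the last given as "After 25s (5s after the previous measurement), a third measurement is made by COBOX". The count closes later: "After 30s, the nursing staff (or arc or tec) enters the number of breaths counted since the start".

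Each of the three COBOX readings is stored with a parallel oximeter result. The device table in section 7 lists that oximeter as "Contec CMS60D Digital Pulse Oximeter (SpO2 - Heart Rate", so it supplies no RR. The RR reference is the manual count alone; section 3 describes it: "this method consists of counting the respiratory movements (inspiration and expiration) of the rib cage for 30 seconds extrapolated to 1 minute", by doubling.

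RR agreement with the manual count is the ranked secondary criterion in section 6. Section 8, Collection of consent, says in general terms that the data will include "HR and FR taken by the COBOX tool at the same time as those of the reference tool". Section 10 (Statistical methods used) makes the readings at T+5 s and T+10 s secondary, in a paragraph about heart rate. No section names the COBOX RR value to be compared with the count, or the length of signal from which COBOX computes RR.

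**The concern.** A value fixed at or before 25 s cannot contain breaths from the last 5 s of the count, whatever algorithm produced it. If one of the listed readings supplies the COBOX RR, the two methods are compared over different stretches of breathing, and part of their difference reflects the timing of the protocol. A wide RR disagreement could then not be cleanly attributed to the device.

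The choice of value is also open. There are three candidate readings, or their mean, and one reference count. If the section 10 ordering carries over from heart rate to RR, the main value would be the 15 s reading, which overlaps the count least. Leaving the choice until the data are in hand is undesirable for a ranked endpoint, particularly as the sponsor performs the analysis (section 15).

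**Working it through.** **Plan's own figure.** No sample size or window is given for RR. The stated size rests on the heart-rate ICC and reproduces: with ρ0 = 0.6, ρ1 = 0.7, k = 3, two-sided α = 0.05 and power 90%, C = (1 + 3×0.6/0.4)/(1 + 3×0.7/0.3) = 5.5/8 = 0.6875, and n = 1 + 2×3×(1.960 + 1.282)²/[2×(ln 0.6875)²] = 225.5, so 226. Then 226/0.70 = 322.9, so 323. Nothing below alters this.

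**Coverage.** Using all signal since the start, the most a reading can cover is 15/30 = 50%, 20/30 = 67% or 25/30 = 83%. At 12–20 breaths/min, 15 s holds 3–5 breaths, against 6–10 in 30 s.

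**Size of the effect.** Inputs:
- Breathing rates of 12 and 20/min are the limits in section 4; 16/min is their midpoint.
- The coefficient of variation (CV) of breath intervals is an assumption, taken as 10–40%. The documents give none.
- COBOX is given no error: its value is the exact fractional number of breaths in its window, scaled to a minute. The reference is whole breaths in 0–30 s, times two.

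Simulating independent gamma-distributed intervals (at least 100,000 runs per cell) gives, at 16/min, the SD of COBOX minus doubled count:

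| COBOX window | CV 10% | CV 20% | CV 30% | CV 40% |
|---|---|---|---|---|
| 0–15 s | 0.93 | 1.34 | 1.78 | 2.26 |
| 0–25 s (cumulative) | 0.80 | 0.94 | 1.07 | 1.22 |
| 0–30 s | 0.77 | 0.82 | 0.82 | 0.82 |

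Over 12–20/min the ranges are 0.86–2.52, 0.76–1.32 and 0.73–0.82.

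The 0–30 s row is the count's resolution. Whole breaths minus fractional breaths has variance of about 1/12 + 1/12 = 1/6, so the doubled count has SD 2×√(1/6) = 0.82.

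**Mismatch alone.** Against the exact 0–30 s rate at 16/min, the SD is 0.53–2.11 for 0–15 s and 0.22–0.86 for 0–25 s. The approximation 60×CV×√[λ(1/T − 1/30)], with λ = 16/60 per second, gives 0.57–2.26 and 0.25–1.01. It is somewhat high, so the simulated values are used.

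**Against the expected spread.** Section 5 expects an SD of 3/min for RR. If that figure excludes mismatch (not stated), the total becomes:
- 15 s: √(9 + 0.53²) = 3.05 to √(9 + 2.11²) = 3.67, or +1.5% to +22%.
- Cumulative 25 s: √(9 + 0.22²) = 3.01 to √(9 + 0.86²) = 3.12, or +0.3% to +4%.

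**Does a 30 s output cure it?** Only if the value compared spans 0–30 s. A cumulative 30 s output leaves no mismatch. With a 15 s trailing window, a 30 s output alone covers only 15–30 s and is no better than the 15 s reading. The mean of the 15 s and 30 s outputs spans 0–30 s exactly and leaves no mismatch. With a 20 s trailing window that mean leaves 0.14–0.78/min over 12–20/min.

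**The case against.** The best reply is that the three readings form a heart-rate schedule. They are set out under the primary endpoint and stored with an oximeter that gives no RR. The parallel start, the general statements of simultaneity and the exclusion "Patient unable to stand for 30 seconds facing the COBOX solution" are all compatible with an RR acquisition running the full 30 s. This stands in part: a reader might infer that the plan commits RR to a reading at 15 to 25 s, and the documents do not establish that. Nor do they list any later COBOX value, and general simultaneity neither supplies one nor selects one. The T+5 s and T+10 s sentence follows a heart-rate sentence, so its bearing on RR is uncertain.

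Second, if COBOX natively reports RR from a short window, its extra variation against a 30 s count is disagreement that users would really meet. That also stands. It would be wrong to treat the whole difference as an artefact of timing, which is why single-reading agreement should still be reported.

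Third, the effect is small in many settings. At CV 10% the mismatch (0.53/min at 15 s) is below the count's own resolution (0.77/min). An error-free device would keep an ICC of at least 0.89 even at 15 s, assuming mean RR 18/min, SD 4, interval CV up to 30% and lag-1 autocorrelation up to 0.5. The protocol expects a coefficient above 0.7. This limits the weight of the point but does not supply the missing specification.

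**Conclusion.** The point holds as a cheap, worthwhile improvement to the ranked RR endpoint. As listed, no COBOX reading spans the reference count, and the COBOX RR value to be compared is unnamed. The consequence for an error-free device at 16/min is an SD of about 0.9–2.3/min (15 s value) or 0.8–1.2/min (cumulative 25 s), against about 0.8/min for a 0–30 s value. Section 4 treats 2 to 3 cycles/min near its risk limits as able to alter a decision, so the effect matters mainly for a short window with irregular breathing. The ranges depend on the assumed CV and on COBOX's unstated window.

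Three stronger conclusions might be inferred and are not supported:
- That the schedule could produce a false validation. The mismatch widens the differences, so it runs against COBOX.
- That COBOX would fail on RR because of it. No RR acceptance limit is set, so no pass or fail consequence follows.
- That the closely spaced readings undermine the heart-rate results. Those readings are time-matched to the oximeter, and section 10 confines its reproducibility claim to repeat readings within one person. The primary endpoint and the size of 323 are unaffected.

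**What to change.** 1. In section 8, add one automatic COBOX RR output at 30 s, stored with the manual count.
2. State the length of signal from which COBOX computes RR.
3. In sections 6 and 10, pre-specify the COBOX value compared with the count as the one covering 0–30 s: the 30 s output if the window is cumulative, or the mean of the 15 s and 30 s outputs if it is a 15 s trailing window. For any other window, name the combination used and acknowledge the remaining mismatch.
4. Where a mean is used, report single-reading agreement beside it, because averaging can reduce device noise and a user sees single readings.

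The cost is a small change to the application's acquisition sequence, handled under Protocol amendment in section 13. The documents do not say whether the study version can already output RR at 30 s, so this must be confirmed. No patient or staff time is added: the count already lasts 30 s and patients must already be able to face COBOX for that long. Items 2 to 4 need only text and a line of analysis.

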- Establish and verify the clinical safety of COBOX and detect any adverse side effects under normal conditions of use of the device and assess whether these constitute an acceptable risk in relation to the expected benefits of the device concerned.
- Evaluate ergonomics and user feedback.
- Evaluate the ease of use of the device (assessed by an ad-hoc questionnaire completed by the caregivers (or arc or tec), one questionnaire per caregiver and per type of device).

Justification of methodological choices

We are carrying out an observational, multicenter, prospective clinical investigation, evaluating the performance of the COBOX device in the context of and within the framework of usual care. Heart rate and respiratory rate are two physiological parameters measured when a patient arrives at the emergency room, so, given the high attendance of these services, it seemed to us to be an excellent place for this study. This measurement is carried out as part of the patient's care pathway using reference technical processes for taking measurements via a CE marked device and a reference method of manual counting. The inclusions of patients consulting in the emergency department make it possible to quickly obtain both a large number of inclusions, and on the other hand, a great variability of the constants noted due to the various pathological states. This approach allows great reproducibility in all clinical situations and thus makes it possible to validate performance in different contexts. In addition, a medico-economic study of the tool will be carried out.

Hypotheses

- H_0 :Routine care measurements in French care services, taken by the COBOX solution are different from measurements obtained through the application of reference technical processes and a manual counting reference method.
- H_1 :The current care measurements in French care services taken by the COBOX solution are consistent with the measurements obtained via the application of the reference technical processes and a reference method of manual counting.

Claims and expected performance of the investigational device that need to be verified.

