Adverse Event: Any harmful manifestation, unintended illness or injury, or untoward clinical sign, including an abnormal laboratory finding, in Participants, Users, or others, in a clinical investigation, related or no to the medical device that is the subject of a clinical investigation.

Serious adverse event: any adverse event resulting in: a) death; b) a serious deterioration in the Participant's state of health, which results in: i) an illness or injury endangering the life of the Participant; ii) a permanent impairment of an anatomical structure or function; (iii) hospitalization or prolongation of the participant's hospitalization; (iv) medical or surgical intervention to prevent any life-threatening illness or injury or permanent impairment of anatomical structure or function; (v) chronic illness; (c) fetal distress, fetal death, congenital physical or mental impairment or birth defect.

Defectiveness of a medical device: any defect in the identity, quality, durability, reliability, safety or performance of a medical device under investigation, including any malfunction, error of use or any defect in the information provided by the manufacturer

In accordance with article 80 of regulation 745/2017 as well as "MDCG-2020-10/1 Safety reporting in clinical investigations of medical devices under the Regulation (EU) 2017/745" and "MDCG 2021-6 Regulation (EU) 2017/745 – Questions & Answers regarding clinical investigation",

Sponsor :

A/ records the following events:

The sponsor records the following data sent to it by the investigator within the time limits specified in point C/ of this document: a) any adverse event defined in the protocol as decisive for the evaluation of the results of the clinical investigation. B) any serious adverse event; c) any defect in an MD which could have led to a serious adverse event in the absence of appropriate measures or intervention, or if the circumstances had been less favourable; d) any new element concerning an event referred to in points a) to c).

B/ declare to the authorities

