10. STATISTICAL ASPECTS

Study size calculation

Considering the results of the performance verification tests of the medical device under study, we have established the study hypotheses in connection with the calculation of the size of the study set out below:

Minimum acceptable value of the ICC correlation coefficient (ρ_0)	0.6
Expected value of the ICC correlation coefficient (ρ_1)	0.7
The number of observations per subject k	3
Two-sided significance level (α)	0.05
Power (1 - β):	90%
Minimum size (n)	226
Size at 30% safety margin	323

A final study size of 323 patients is retained; taking into account a rate of unusable data of 30% in order to maintain the statistical power of the study in the event of exclusion of outliers.

Statistical methods used

The analysis will carry an initial descriptive part. The qualitative variables will be expressed in frequencies (with their 95% CI), and the quantitative variables expressed in means (with their standard deviation) if the distribution is normal. Otherwise, the quantitative variables will be expressed as the median (with their interquartile range).

Then, we will perform a comparative analysis, using chi 2 tests (or Fisher's exact) for the qualitative variables and student test (or Mann-Whitney test if applicable) for the quantitative variables. For performance estimation, we will determine the intra-class correlation coefficient with its confidence interval and we will perform a graphical analysis of Bland and Altman. In addition, we will calculate the mean square errors between the measurement with COBOX and the reference measurements, and they will be expressed as a percentage.

All our analyzes will be carried out at the 5% significance level.

An analysis of the repeated and compared measurements between COBOX and the CE marked device (used during the technical reference process for taking measurements) for the heart rate will make it possible to evaluate the reproducibility of the COBOX on repeated measurements in the *COBOX Protocol Valid*

same individual. A secondary statistical analysis will be done for the measurement times T+5s and T+10s.

We will use imputation methods or sensitivity analysis for the management of missing data.

11. Access rights to source data and documents

Access to data

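### The safety objective covers any side effect of COBOX, but non-serious adverse events and device failures without serious-event potential have no planned route to be recorded or counted

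*Combined protocol and SAP*

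**What the plan says.** **Objective.** Section 1 (Goals) and section 5 (Secondary objectives) set the aim: "Establish and verify the clinical safety of COBOX and detect any adverse side effects under normal conditions of use of the device". The same item asks whether any such effects are an acceptable risk given the expected benefits.

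**Definitions.** Section 9 defines both terms broadly. An adverse event is "Any harmful manifestation, unintended illness or injury, or untoward clinical sign, including an abnormal laboratory finding, in Participants, Users, or others", whether or not related to the device. A device defect is "any defect in the identity, quality, durability, reliability, safety or performance of a medical device under investigation"; malfunctions and mistakes by the user are expressly covered.

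**Recording rule.** List A/ in section 9 then has the sponsor record four things:

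- a) "any adverse event defined in the protocol as decisive for the evaluation of the results of the clinical investigation";
- b) adverse events that meet the definition of serious, related or not;
- c) among device defects, only those described as "any defect in an MD which could have led to a serious adverse event in the absence of appropriate measures or intervention", a test that also extends to what could have happened in worse circumstances;
- d) new information on a) to c).

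List A/ is tied to the deadlines in point C/, where the investigator has at most 3 calendar days to report to the sponsor.

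**The concern.** The objective and the definitions are wide, and the recording rule is narrow. Item a) is the only one through which a non-serious adverse event could enter. It depends on the protocol naming events as decisive, and no section in the text available does so. Section 4 (Potential side effects) reports that none has been identified to date, so it cannot serve as that list either.

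If sites follow the rule as written, a patient or user with a non-serious event leaves no trace in the study data. Nor does a COBOX failure that could not have led to a serious event have to be logged as a deficiency. The final report could then state that no non-serious side effect was seen, and a reader would take this as evidence on safety when nobody was asked to record such effects.

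**Working it through.** **1. Is there another route?** Each section that could fill the gap was compared with the objective.

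| Place | What it provides |
|---|---|
| Section 6, primary and secondary endpoints | No safety endpoint |
| Section 8, summary of patient follow-up | Steps for COBOX, oximeter and breath count; no adverse-event or failure field |
| Section 8, collection of consent (data list) | Heart and respiratory rates by both methods, age, sex, phototype |
| Section 10, statistical methods | No safety analysis |
| Section 12, research follow-up | The technician's safety task is to pass on serious adverse events |
| Section 14, sponsor archive | The only safety documents named concern serious adverse events |
| Section 3 (traceability) and section 7 (device management) | Optional server monitoring, tablet replacement, bug fixes; no required log or count |

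Section 12 (Guidelines for data collection) requires everything the protocol asks for to be entered in dedicated boxes on the tablet. No box for safety or failure is described. None of these places supplies the missing record.

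**2. The plan's own denominator.** The safety objective has no stated figure. The only design calculation is the sample size in section 10, with ρ0 = 0.6, ρ1 = 0.7, k = 3, two-sided α = 0.05 and power 90%. The usual formula for an intraclass correlation is

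n = 1 + 2k(z₁₋α/₂ + z₁₋β)² / [(k − 1)(ln C)²], with C = [1 + kρ0/(1 − ρ0)] / [1 + kρ1/(1 − ρ1)].

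- C = (1 + 1.8/0.4) / (1 + 2.1/0.3) = 5.5/8 = 0.6875.
- n = 225.5, rounded up to 226, as stated.
- 226/0.70 = 322.9, rounded up to 323, as stated.

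**3. What 323 patients could show with complete recording.**

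Exact upper limit if no event is seen:

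- one-sided 95%: 1 − 0.05^(1/323) = 0.92%;
- two-sided 95%: 1 − 0.025^(1/323) = 1.14%.

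Chance of seeing at least one event, 1 − (1 − p)^323, for assumed true rates p (the documents give none):

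| Assumed rate | Chance of at least one event |
|---|---|
| 0.5% | 80.2% |
| 1% | 96.1% |
| 2% | 99.9% |

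The planned size is therefore adequate to say something useful about non-serious events. These figures need every event to be recorded. The rule does not ensure that for non-serious events or for defects outside item c), so none of the figures can be claimed for them.

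**The case against.** The strongest reply is that much of what matters is already captured.

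- **Serious events.** Item b) records every serious adverse event, related or not. A reader might infer that the plan would report no side effects whatever happened. The text does not support that, and a limit for serious events can be stated.
- **Wrong readings.** A reader might also infer that inaccurate readings escape notice. They do not. Section 8 stores each COBOX reading with its paired oximeter value, and section 10 analyses the differences by intraclass correlation, Bland-Altman plot and mean square error. What is missing is a reason code and a planned count of failed or missing readings.
- **Item c).** Section 4 says "the information provided by COBOX will not be used in clinical decision-making", which makes it tempting to say that almost no failure could meet the serious-event test. But that test also covers worse circumstances than those that occurred, so a grossly wrong heart rate might qualify. How many failures would qualify is a matter of interpretation and is not shown to be near zero.
- **The 30% allowance.** Section 10 links it to exclusion of outliers. It is not a device-failure rate, and the documents give no such rate.
- **Wider wording in point C/.** Its general reference to events and defects could be read as all of them. Read in sequence it points back to lists A/ and B/. If it is meant more widely, it conflicts with A/ and the two need reconciling.
- **User feedback.** Section 5 plans an evaluation of ergonomics and user feedback, with one questionnaire per caregiver and device type. This is not a per-patient record of events.
- **Low risk.** The device is contactless and the measurement lasts about 30 seconds, so few events are expected. That is plausible, but the sponsor set the objective, and an expectation of few events does not replace counting them.

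These replies narrow the point. They do not supply a record of non-serious events or of deficiencies without serious-event potential.

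**Conclusion.** The point holds in this limited form. For non-serious adverse events, and for device deficiencies that could not have led to a serious event, there is no planned route to record or count them and no stated safety endpoint or analysis. That part of the secondary objective cannot be answered, and an absence of reports could not support a conclusion of acceptable risk.

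The size of the loss is the statement the study could otherwise make: with 0 of 323, an upper limit of 1.14% (two-sided 95%) or 0.92% (one-sided). This assumes that all 323 patients are assessed and counted, including those whose readings are unusable for the agreement analysis. It covers only events seen during the session, since participation lasts under 30 minutes.

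The finding that no decisive event is defined rests on the text available for review, from which some pages had been removed. The primary heart-rate analysis and the sample size are not affected. The change should be made, but it does not threaten the main result.

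**What to change.** 1. **Leave expedited reporting as it is.** Keep lists A/ and B/ and the deadlines in point C/. Widening list A/ itself would put every non-serious event and every failed reading under the 3-day investigator report, in emergency patients who already arrive with symptoms.
2. **Add one mandatory end-of-session tablet field** to section 8, in both the follow-up steps and the data list. It should record any adverse event in the participant or user (yes/no, description) and any COBOX deficiency or failed reading under the section 9 definition (yes/no, reason). This is study data outside the 3-day report unless the entry meets list A/.
3. **Add two endpoints** to section 6 and their analysis to section 10: the proportion of patients with any adverse event, and the proportion with any deficiency or failed reading, each with an exact 95% confidence interval. Section 10 already plans frequencies with 95% intervals for qualitative variables. The exact form matters because counts may be zero or close to it. Count patients rather than readings, because the three readings from one patient are not independent.

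**Cost.** Protocol wording, one short tablet screen and a few seconds per patient, with no extra patients or visits. A non-zero deficiency rate may have to be reported.
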